4.1 Treatment

Initial treatment consists of the randomly-assigned surgery as described in chapter 3.

Following the surgery, nonsurgical treatment of any overcorrection, undercorrection, or deviations associated with diplopia is at investigator discretion at any time during the study, with the following stipulation:

- If at the 8 week visit a constant esotropia at least 6 PD by SPCT at distance and near is present, the condition must be managed with prism (*section 4.4.1*).

Reoperation or treatment with botulinum toxin is not permitted during the first 6 months following surgery. After the 6-month exam, a patient may undergo reoperation or treatment with botulinum toxin only after criteria for surgical failure are met (*section 4.5.1*).

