1519 overminus: the Preschool Randot at near score to be used for the outcome classification will
1520 be the one tested *without* wearing prism or overminus. If this measurement shows a decrease
1521 of at least 2 octaves (at least 0.6 log arcsec) from the enrollment measurement, or to nil, to
1522 avoid adding to testing burden and to the complexity of visits, a confirmatory retest *is not*
1523 needed to be considered a surgical failure for this analysis.

~~1524~~

1526 **6.3.2 Exploratory Analyses in Patients with Baseline Angle > 40 to 50 PD**

1527 Additional exploratory analyses will be stratified by IXT type and conducted in a secondary
1528 cohort of patients whose largest angle by PACT at enrollment is > 40 to 50 PD.
1529

1530 The proportion of patients with surgical failure by 3 years will be calculated and will be
1531 compared between treatment groups using the same method as for the primary analysis.
1532

1532

1533 **6.4 Safety Analyses**

1534 Postoperative complications will be tabulated according to treatment group.

1535

1536 **6.5 Additional Tabulations and Analyses**

1537 The following will be tabulated according to treatment group:

- 1538 1. Baseline demographic and clinical characteristics
- 1539 2. Baseline data for study completers vs. non-completers
- 1540 3. Protocol deviations

1541

1542 A flow chart will be constructed that accounts for all subjects. Visit completion rates will be
1543 tabulated according to treatment group for each visit. The percentage of subjects with visits
1544 completed in window, out of window, and missed for each visit will be tabulated.

1545

1546 **6.6 Interim Analysis**

1547 There are no plans to formally assess surgical failure at a timepoint earlier than 3 years because it
1548 is the long-term outcome that is of clinical interest and because the treatment groups are
1549 expected to differ in the timing of surgical failure and in the criteria met for surgical failure.

1550 Patients receiving unilateral lateral rectus recession with medial rectus resection (R&R) are
1551 expected to fail earlier, due primarily to consecutive esotropia (i.e., overcorrection) which cannot
1552 be managed with prism, whereas patients receiving bilateral lateral rectus recessions (BLRrec)
1553 are expected to have better short-term motor outcomes but fail later, due primarily to recurrence
1554 of the intermittent exotropia over the long term. A treatment group comparison of failure

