68 the first occurrence of *any* suboptimal outcome criterion (or re-operation) being met, whereas the cause-
69 specific outcomes refer to the first occurrence of the *particular* suboptimal outcome criterion being met,
70 and 2) reoperation prior to meeting a particular suboptimal outcome criteria was considered an *suboptimal*
71 *outcome* for the primary analysis but was censored as a *non-outcome* in the analysis that evaluated cause-
72 specific outcomes. For each of the three cause-specific outcomes, participants who met criteria *other than*
73 *the particular criteria being assessed* remained “at risk” for the criterion of interest unless they underwent
74 reoperation. For example, participants who met the stereo loss outcome remained “at risk” for the
75 exotropia and constant esotropia outcomes until they either met them or underwent reoperation. The
76 cumulative probability of each cause-specific outcome by 3 years and a 95% CI were obtained using the
77 K-M method. It is acknowledged that the three cause-specific outcomes are not independent because
78 reoperation is a competing risk for each (e.g., participants who met the exotropia outcome and underwent
79 reoperation were no longer at risk for meeting stereo loss or constant esotropia outcomes).

80
81 The cumulative probability (and 95% confidence interval) of each cause-specific outcome will be
82 determined using Kaplan-Meier method.

83
84 **Table 1: Three Objective Criteria for Surgical Failure**

Based on a masked exam occurring between 6 months and 3 years after randomization:

1. **Exotropia** at distance OR near at any time during the exam (i.e., can be constant or intermittent; determined by a cover/uncover test) with a magnitude of atleast 10 PD by SPCT, confirmed by a retest
2. **Constant esotropia** at distance OR near (determined by at least 3 cover/uncover tests—one must be before any dissociation) with a magnitude of atleast 6 PD by SPCT, confirmed by a retest
3. Decrease in Preschool Randot near **stereoacuity** atleast 2 octaves (atleast 0.6 log arcsec) (*see Table 3*) from the enrollment measurement, or to nil, confirmed by a retest

Baseline stereoacuity at enrollment, in arcsec	Level needed at follow up visit to meet surgical failure criteria, in arcsec
40"	200" or worse
60"	400" or worse
100"	400" or worse
200"	800" or worse
400"	Nil

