3. Get cumulative probability of each cause-specific suboptimal surgical outcome by 3 years for each treatment group from Kaplan-Meier (K-M) survival analysis.
4. Compare cumulative probability of each cause-specific suboptimal surgical outcome by 3 years between treatment groups using a two-sided Z-test.
5. Calculate the treatment group difference (and 95% CI) in the cumulative probability of each cause-specific suboptimal surgical outcome 3 years.

289
290

Technical plan

291
292
293
294
295
296
297
298
299
300
301
302

1. Define three causes of meeting suboptimal outcome criteria:
 - **Exotropia** at distance OR near at any time during the exam (i.e., can be constant or intermittent; determined by a cover/uncover test) with a magnitude of atleast 10 PD by SPCT, confirmed by a retest
 - **Constant esotropia** at distance OR near (determined by at least 3 cover/uncover tests—one must be before any dissociation) with a magnitude of atleast 6 PD by SPCT, confirmed by a retest
 - Decrease in Preschool Randot near **stereoacuity** atleast 2 octaves (atleast 0.6 log arcsec) (*see Table 3*) from the enrollment measurement, or to nil, confirmed by a retest

Table 1: Preschool Randot Stereotest

Baseline stereoacuity at enrollment, in arcsec	Level needed at follow up visit to meet surgical failure criteria, in arcsec
40''	200'' or worse
60''	400'' or worse
100''	400'' or worse
200''	800'' or worse
400''	Nil

303
304
305
306
307
308
309

311
312

level time-to-event outcome for meeting the criterion at any time by 3 years.

Rules for Classification of Each Cause Specific Outcome

- a. Patients who meet the specified criterion at any time without having first undergone reoperation are counted as having met the outcome the first time the specific outcome occurs, regardless of whether any other suboptimal surgical outcome criterion was met at any time.

2. For each of these three causes, create a separate patient -

- 313 b. Patientswhounderogoreoperationwithoutfirstmeetingthespecifiedcriterion will be considered
 314 not to have met the outcome and will be censored at the reoperation date month (i.e. the
 315 end of their ‘uncontaminated’ time).
- 316 c. Patientswhodonotmeetthespecifiedcriterionby3yearsandhavenotundergonereoperation are right-
 317 censored for the specified outcome at the last visit date.
- 318
- 319 d. Patientswhomeetcriteriaotherthanthespecifiedcriterion(e.g.exotropiaorconstant esotropiawhen

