363 CREATE MACRO TO GET K-M CUMULATIVE PROBABILITY OF A GIVEN OUTCOME BY 3 YEARS
364 *****/
365
366 %macro kmestimates (outcome, outcometime);
367
368 title1 "K-M Survival Analysis for '&outcome' Outcome";
369
370 proc lifetest data = roster method=km outsurv=failresults stderr plots=none alpha=.05;
371     time &outcometime*&outcome(0);
372     strata trtgroup;
373
374 run;
375
376 data failresultCIs;
377     set failresults;
378     /* create failure estimates (rather than survival)*/
379     failure = round ((1-survival), 0.01);
380     failureLCL = round ((1-SDF_UCL), 0.01);
381     failureUCL = round ((1-SDF_LCL), 0.01);
382     /* limit to records where the survival estimate has changed
383     (i.e. records where the CI is not null) */
384     if SDF_LCL NE . then output;
385     label failure = "Cum. probability of '@outcome' Outcome";
386     label failureLCL = "Lower limit of CI for Cum. probability of '@outcome' Outcome";
387     label failureUCL = "Upper limit of CI for Cum. probability of '@outcome' Outcome";
388
389 run;
390 %sort (failresultCIs, trtgroup);
391 proc print data = failresultCIs;
392     by trtgroup;
393     title2"Review Output Dataset from K-M Survival Analysis for '&outcome' Outcome";
394 run;
395
396 %mend;

```

3. Compare cumulative probability of each cause-specific outcome by 3 years for each treatment group using code to perform a Z-test. Manually input probabilities and standard error for each outcome (get from K-M output).

```

402 /* Calculate Z-Test */
403
404 /* Need to manually input probabilities and standard error for each outcome
405 (get from K-M output) */
406
407 data check;
408     length outcome $20;
409     input outcome probblr seblr probrr serr;
410     datalines;
411     exofail 0.#### 0.#### 0.#### 0.####
412     conesofail 0.#### 0.#### 0.#### 0.####
413     stereofail 0.#### 0.#### 0.#### 0.####
414 ;
415
416 run;
417
418 /* note that 0.#### is a placeholder for use in SAP. Actual values taken from K-M output */
419
420 data check;
421     set check;
422     diff = probblr - probrr;
423     sumofsquaredse = sqrt (seblr**2+serr**2);
424     cilower = diff - (1.96*sumofsquaredse);
425     ciupper = diff + (1.96*sumofsquaredse);

```

```
424         zscore = diff/sumofsquaredse;
425         pvalue = 2*(1 - probnorm(abs(zscore)));
426     run;
427
428     proc print data = check noobs;
429         var outcome probblr seblr probrr serr sumofsquaredse diff cilower ciupper zscore pvalue;

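### The 2018 SAP censors reoperation, calls it a competing risk, and still reports 1 minus Kaplan-Meier as the 3-year probability of each cause-specific outcome; it needs a correct label and a cumulative-incidence estimate beside it (the effect is probably small)

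*SAP*

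**What the plan says.** SAP (May 2018) section 1.3 defines three post hoc secondary outcomes: meeting the exotropia, the constant esotropia or the stereoacuity-loss criterion by 3 years. A child who meets a different criterion stays at risk until reoperation. The text concedes that the three outcomes are not independent because "reoperation is a competing risk for each (e.g., participants who met the exotropia outcome and underwent" reoperation could no longer meet the other two. The "cumulative probability of each cause-specific outcome by 3 years and a 95% CI were obtained using the" Kaplan-Meier method.

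Objective #2, rule b, treats a child reoperated before the criterion as "not to have met the outcome and will be censored at the reoperation date month (i.e. the" close of that child's uncontaminated time). The macro's time statement, "time &outcometime*&outcome(0"), has one event and one censoring value. It outputs 1 minus survival under a cumulative-probability label. Step 4 is to "Compare cumulative probability of each cause-specific suboptimal surgical outcome by 3 years between treatment groups using a two-sided Z-test", and step 5 adds the difference with a 95% CI. Neither SAP plans a cumulative-incidence estimate.

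Two protocol statements bear on the censoring. Section 4.1 says that after the 6-month exam "a patient may undergo reoperation or treatment with botulinum toxin only after criteria for surgical failure are met"; section 4.7 allows an exception for unmanageable esotropia before that exam. Section 6.6 says the arms are "expected to differ in the timing of surgical failure and in the criteria met for surgical failure": R&R patients are "expected to fail earlier, due primarily to consecutive esotropia (i.e., overcorrection) which cannot" be managed with prism, and BLRrec patients are expected to fail later, mainly by recurrent exotropia.

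**The concern.** Most readers will take a 3-year cumulative probability of, say, the exotropia outcome as the share of children who met it. With the competing event censored, 1 minus Kaplan-Meier is not that share. It spreads the later risk of the remaining children over those already reoperated, so it is larger whenever some reoperations precede later events.

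The other reading is risk in the absence of reoperation, which the SAP's idea of uncontaminated time suggests. That is a reasonable target, but it is identified only if reoperated children would otherwise have had the same later risk as those still followed. The SAP does not state this assumption. It is doubtful because reoperation generally follows a failure criterion, and SAP (March 2017) section 1.7 says the decision is the unmasked investigator's and could be related to treatment group.

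At stake is the description of how each procedure fails. If the pattern in Protocol 6.6 holds, more R/R than BLR children may be reoperated before they could meet the exotropia criterion, so the distortion need not be equal in the two arms.

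**Working it through.** **Inputs.** No cause-specific figure can be reproduced, because Objective #2 of the May 2018 SAP holds placeholders. The March 2017 SAP (Objective #2, step 10) gives primary failure by 3 years as 0.4594 (SE 0.0518) in BLR and 0.3731 (SE 0.0520) in R/R. These are pre-closeout values that were later rerun. The arms have 101 and 96 children. Reoperation rates are not given and are assumed below.

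**Cap.** Let c be the proportion who meet the criterion before any reoperation and r the proportion reoperated before meeting it. The two groups do not overlap, and both count as primary failures. So c + r ≤ 0.4594 (BLR) or 0.3731 (R/R), subject to the sampling error of those estimates.

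**Excess, constant hazards.** 1−KM = 1 − (1 − c − r)^(c/(c+r)), and the excess is 1−KM minus c.

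**Excess, extreme ordering.** If every reoperation precedes every event, 1−KM = c/(1 − r).

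| c | r | 1−KM, constant hazards | Excess (points) | Excess, extreme ordering (points) |
|---|---|---|---|---|
| 10% | 5% | 10.27% | 0.27 | 0.53 |
| 10% | 10% | 10.56% | 0.56 | 1.11 |
| 20% | 5% | 20.56% | 0.56 | 1.05 |
| 20% | 10% | 21.16% | 1.16 | 2.22 |

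For the second row: (1 − 0.20)^(0.10/0.20) = 0.8944, so 1−KM = 0.1056.

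**Maximum under the cap.** With constant hazards:
- BLR peaks at c = 21.8%, r = 24.1%: 1 − 0.541^(0.218/0.459) = 25.3%, an excess of 3.5 points.
- R/R peaks at c = 17.9%, r = 19.4%: 1 − 0.627^(0.179/0.373) = 20.1%, an excess of 2.2 points.

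In the extreme ordering with c + r = T, the excess c·r/(1 − r) is largest at r = 1 − √(1 − T), where it equals r². This gives 0.2647² = 7.0 points in BLR and 0.2082² = 4.3 points in R/R.

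**Visit-based check.** Take a 2% criterion risk at each of six visits, with reoperation between visits removing 10% in total. Then 1−KM = 11.42% against an actual incidence of 10.85%, an excess of 0.57 points, close to the 10%/10% row.

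**Between arms (assumed rates).**
- Equal 10% incidence, 15% against 5% reoperated first: 10.87% against 10.27%, a spurious 0.6 points. A simple binomial SE of the difference is √(0.09/101 + 0.09/96) = 4.3 points, so the shift is 0.14 SE.
- Equal 15% incidence, 20% against 5%: 16.86% against 15.41%, a spurious 1.45 points. The SE is √(0.1275/101 + 0.1275/96) = 5.1 points, so the shift is 0.28 SE.

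**The trade-off in the other direction.** Suppose the no-reoperation risk is 20% in both arms, with 5% against 15% reoperated first. Solving the constant-hazards formula for c gives 19.5% against 18.3%: cumulative incidence differs by 1.1 points (before rounding) where 1−KM shows no difference.

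**The case against.** The SAP is open about what it does. It states the censoring, defines the risk set, names the competing risk and admits the dependence, and rule b points toward risk without reoperation. Other planned work gives context: reoperation by 3 years by arm, the association between treatment group and reoperation among those meeting failure criteria (SAP March 2017, sections 1.6 and 1.7), and the 3-year status tabulations (SAP May 2018, section 1.7). The outcomes are post hoc and secondary. All of this stands, and it limits the point to a label and a companion estimate. It does not remove the point: disclosing the censoring does not change the reported percentage, and none of those outputs gives the proportion reoperated before each criterion.

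A second objection also stands. Testing cumulative incidence would put the unmasked reoperation decision into the between-arm contrast, as the last calculation shows. Kaplan-Meier carries the risk of dependent censoring instead. Neither dominates, so a reader who infers that the Z-test must move to cumulative incidence goes further than the documents support.

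Third, examinations continue after reoperation (Protocol 4.5.1 and 4.7), so incidence regardless of reoperation is also a possible target. Cumulative incidence before reoperation is therefore one choice; it is the one that matches the SAP's decision to end risk at reoperation.

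Finally, the largest excesses are corner cases. The BLR maximum needs every failure that does not meet the criterion to be reoperated first.

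**Conclusion.** The point holds as one of labelling and a missing estimate. As the proportion who actually met a criterion before reoperation, the planned figure is biased upward. As risk without reoperation, it rests on an unstated and doubtful assumption of independent censoring, and the error could then go either way.

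The excess in a per-arm percentage is likely around 0.3 to 1.2 points if incidence is 10–20% and 5–10% are reoperated first; those rates are assumptions. The caps of 3.5 (BLR) and 2.2 (R/R) points hold only under constant hazards. Because Protocol 6.6 expects timing to differ, they should not be read as absolute; the extreme ordering gives 7.0 and 4.3.

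A reader might infer that the arm comparison is seriously distorted, or that the trial's main result is affected. The documents support neither. Plausible shifts in the difference are a small fraction of its standard error, and reoperation counts as failure in the primary analysis.

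**What to change.** - Label the Kaplan-Meier figure as the 3-year risk in the absence of reoperation, assuming independent censoring.
- Beside it, by arm and with a 95% CI, report the Aalen-Johansen cumulative incidence with reoperation before the criterion as the competing event. Label it the observed 3-year probability of meeting the criterion before reoperation.
- Include botulinum toxin in the competing event only after confirming that the treatment records capture it. Rule b names reoperation alone, and the patient-level flag in the March 2017 SAP is set from REOPERATION = 1.
- Tabulate, by arm, the proportion reoperated before each criterion.
- The Z-test may stay on the Kaplan-Meier estimates, with the cumulative-incidence difference and its CI as a companion.

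The cost is one more status code, built from the reoperation flag and date already held, and one more table column. The downside is that the cumulative-incidence difference also reflects any difference between arms in reoperation, which is why both estimates should be shown.

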1.4 Secondary Analysis – 3-Year Stereoacuity

Secondary outcomes of 3-year stereoacuity (distance and near) will be assessed in all patients who complete the 3-year visit. The 3-year visit stereoacuity will be analyzed regardless of what treatment(s) a patient has received and regardless of whether the patient has undergone reoperation. These 3-year stereoacuity outcomes will be analyzed as continuous variables and compared between treatment groups using analysis of covariance (ANOVA) models that adjust for the corresponding baseline stereoacuity.

1.5 Complete or Near-complete Resolution at 3 Years

Complete or near-complete resolution at 3 years was defined post hoc as meeting all of the following at the 3-year visit:

1. Exodeviation <10 PD (tropia, phoria, or no deviation) by both SPCT and PACT at distance and near and ≥ 10 PD reduction in PACT magnitude from distance and near angles at enrollment provided the corresponding angle was at ≥ 10 PD at baseline.
 - This criterion was originally written as ≥ 10 PD reduction in PACT magnitude from *largest of* distance and near angles at enrollment. After asking the protocol chairs to clarify which angle needed to be reduced by ≥ 10 PD at 3 years in cases where the distance and near angles at enrollment are the same magnitude (i.e. neither is the ‘largest’), it was decided that both angles should be reduced by ≥ 10 PD in order to meet the criterion, if the angle was at ≥ 10 PD at baseline, OR should be reduced to orthodeviation (0 PD) if the angle was at <10 PD at baseline. *Note that because all patients in the basic primary cohort have distance and near PACT ≥ 10 PD, this caveat is not cited in the manuscript as being part of the criteria. Only one patient in one of the secondary cohorts was <10 PD at baseline—a 3 PD near angle which was ortho at 3 years.* The revised criterion was extended to all patients, not only those whose enrollment PACT was the same magnitude at distance and near, for consistency. For example, if a patient with 20 PD at distance and near at baseline is required to have a reduction ≥ 10 PD at both distance and near at 3 years in order to be eligible to meet complete or near-complete resolution, then a patient with 25 PD at distance and 15 PD at near should also be required to have both reduced by ≥ 10 PD at 3 years, otherwise the first patient is being penalized simply for having the same measurement at both distances.
2. Esotropia <6 PD (tropia or no tropia, *note that phoria does not apply to SPCT*) at distance and near by SPCT
3. No decrease in Preschool Randot stereoacuity of ≥ 2 octaves from the enrollment stereoacuity or to nil
4. No reoperation or treatment with botulinum toxin
5. No non-surgical treatment for a recurrent or residual exodeviation

Although complete or near-complete resolution was specified post hoc, a three-level failure/indeterminate/success outcome was prespecified in the protocol; the only difference between the “success” level and “complete or near-complete resolution” is that patients who met suboptimal outcome criteria at a previous visit but not at the 3-year visits were considered failures in the pre-specified outcome but could potentially be considered complete or near-complete resolutions if all other criteria were met.

127 The treatment group difference in the proportion of participants with complete or near complete resolution
128 at 3 years was compared using Barnard’s exact test and calculating a 95% CI using Farrington-Manning
129 scores. Originally the Fisher’s exact test was used, but the corresponding exact CI is calculated in a way
130 in SAS that would permit potential disagreements on statistical significance between p values of <0.05
131 and the 95% CI, whereas Barnard’s test and Farrington-Manning scores for the 95% CIs will agree on
132 statistical significance.

133
134 Note that complete or near-complete resolution *without meeting suboptimal surgical outcome at any time*
135 was also reported in the manuscript (consistent with the prespecified “success” criteria in the protocol)
136 and compared between treatment groups using similar methods.

137 138 **1.6 IXT Questionnaire (IXTQ)**

139 For the IXTQ proxy questionnaires and for each of the three parent questionnaire subscales (psychosocial,
140 functional, and surgical), mean Rasch-based QOL scores at 3 years were compared between treatment
141 groups using linear regression models adjusting for the baseline score.

142 For the IXTQ child questionnaire, because some participants were too young for the IXTQ at baseline
143 (those enrolled 3-<5 years of age) and because some children completed the 5 to 7-year old IXTQ version
144 at baseline and the 8 years and older version at 3 years, the two age versions were evaluated separately
145 and mean QOL scores at 3 years were compared between treatment groups using linear regression models
146 that did not adjust for baseline. Because the Rasch scores can be difficult to interpret, the mean of the 0 to
147 100 scores based on the Rasch scores will be cited as the mean in each treatment group.

148
149 The assumptions of ANOVA/ANCOVA will be tested and if violated, a non-parametric test such as
150 Wilcoxon rank sum test will be used.

151 152 153 **1.8 Nonsurgical Treatment**

154 Postoperative nonsurgical treatment for XT, ET, and/or diplopia was tabulated for each treatment group.
155 Because the reason for this nonsurgical treatment was not specified other than being prescribed for IXT,
156 ET, or diplopia, the type of deviation that was present when the nonsurgical treatment was prescribed was
157 reported. This data was used to report the proportions of participants with non-surgical treatment
158 prescribed when exodeviation was present, when esodeviation was present and when exodeviation and
159 esodeviations were present at different times during the study. Among participants who met the constant
160 esotropia suboptimal surgical outcome during the study, the proportion who had nonsurgical treatment
161 prescribed was reported.

162 163 **1.7 Additional Tabulations and Analyses**

164 The following will be tabulated for each treatment group:

- 165 • Baseline demographic and clinical characteristics
- 166 • Baseline demographic and clinical characteristics for study completers vs. not
 - 167 ○ Study completion refers to patients who completed the 3-year visit or were withdrawn
 - 168 from the study after they met the primary outcome of suboptimal surgical outcome (for
 - 169 meeting objective criteria or for reoperation). It does not include patients who were
 - 170 withdrawn from the study without ever having met primary outcome of suboptimal
 - 171 surgical outcome.
- 172 • Percentage with completion of each follow up visit

173
174
175
176
177
178
179
180
181
182
183
184
185
186
187

- Listing of each complications that occurred either during surgery, or were reported at the 1-week or the 8-week postoperative visits
- Outcomes for participants meeting exotropia or esotropia suboptimal outcome criteria
 - Separately for participants who met the exotropia and esotropia components of suboptimal outcome criteria, the proportion out of those meeting the criterion who received nonsurgical treatment, and the proportion of non-reoperated cases in which the criterion of interest was not present at 3 years was reported.
- In subjects who completed the 3-year visit, 3-year status was evaluated according to whether suboptimal surgical outcome had occurred before 3 years
 - 3-year status was defined as: reoperation before 3 years, suboptimal surgical outcome at 3 years, complete or near-complete resolution at 3 years, or non-reoperated and meeting neither suboptimal surgical outcome or complete or near-complete resolution at 3 years.
 - Timing of suboptimal surgical outcome was categorized as: never met suboptimal surgical outcome, suboptimal surgical outcome before 3 years, suboptimal surgical outcome met only at 3 years

188 **Datasets/Databases Used**

189 **SOURCE DATASETS/DATABASES USED TO CREATE FINAL IXT1 DATASETS**

191 **PREVIOUSLY VERIFIED SAS DATASETS CREATED FOR ESA 2017 PRESENTATION**

193 **BASELINE** - one-record per baseline exam for all patients enrolled into in IXT1 (regardless of
194 whether randomized) N=277
195 Location: F:\user\PEDIG\Manuscripts-Presentations\Manuscripts\IXT\IXT1\Manuscripts\Primary
196 MS\Datasets\8-23-17 (verified)

198 **MASKEDEXAMS** - one-record per IXT1 masked exam (protocol-specified or unspecified) that
199 was at least partially completed IXT1 N=1344
200 Location: F:\user\PEDIG\Manuscripts-Presentations\Manuscripts\IXT\IXT1\Manuscripts\Primary
201 MS\Datasets\8-23-17 (verified)

203 **ROSTER** – one-record per randomized patient analysis dataset N=265
204 Location: F:\user\PEDIG\Manuscripts-Presentations\Abstracts and Presentations\ESA\ESA
205 2017\IXT1\Dataset\8-21-17

207 Note that the above permanent datasets include all IXT1 patients, but the analysis was limited to
208 the primary cohort of basic-type IXT participants with angles ranging from 15 to 40Δ (N=197).

210 **IXTQ.IXTQALL_19OCT2017** – one-record per IXTQ completed at any visit in IXT1 and IXT2
211 studies (N = 4790)
212 Location: F:\user\PEDIG\Manuscripts-Presentations\Manuscripts\IXT\IXT2\IXTQ\Manuscript
213 Analysis\Datasets

- 214 • Note that the above permanent dataset was created by taking a previously-verified program
215 using IXT2 data and re-running to read in data from both IXT1 and IXT2 (discussed at 2/13/18
216 manuscript meeting and confirmed that no additional verification is required). Note that the
217 dataset includes all IXTQs completed at any visit in IXT1 and IXT2 studies; however, only
218 data from enrollment and 3-year visits for IXT1 patients was added to the IXT1 final dataset.

220 _____
221 **POST CLOSEOUT SQL DATABASE: PEDIG_IXT1_3yrCloseout_20jun2017**

223 _____
224
225

226 **FINAL DATASETS CREATED**

227

ROSTER – one-record per randomized patient in IXT1 N=265

228

Location: F:\user\PEDIG\Manuscripts-Presentations\Manuscripts\IXT\IXT1\Manuscripts\Primary
MS\Datasets\##-18

229

230

231

MASKEDEXAMS - one-record per IXT1 masked exam (protocol-specified or unspecified) that
was at least partially completed IXT1 N=1344

232

233

Location: F:\user\PEDIG\Manuscripts-Presentations\Manuscripts\IXT\IXT1\Manuscripts\Primary
MS\Datasets\##-18

234

235

236

BASELINE - one-record per baseline exam for all patients enrolled into in IXT1 (regardless of
whether randomized) N=277

237

238

Location: F:\user\PEDIG\Manuscripts-Presentations\Manuscripts\IXT\IXT1\Manuscripts\Primary
MS\Datasets\##-18

239

240

241

242 *Note that ##-18 is placeholder for date of final run for final datasets.*

243

244

245
246
247
248
249
250
251
252
253
254
255
256
257
258
259
260

List of Objectives

Objective #1: Define the cohort of interest

Objective #2: Determine the cumulative probability of meeting each of the three cause-specific suboptimal surgical outcome criteria by 3 years (post hoc outcome)

Objective #3: Compare 3-year stereoacuity between BLR and R/R treatment groups

Objective #4: Compare complete or near-complete resolution at 3 years between BLR and R/R treatment groups

Objective #5: Compare 3-year IXT Questionnaire (IXTQ) scores between treatment groups

Objective #6: Tabulate non-surgical treatment prescribed for BLR and R/R treatment groups

261
262
263
264
265
266
267
268
269
270
271
272
273

Objective #1: Define the cohort of interest

1. 197 patients with basic-type IXT with largest preoperative exodeviation between 15 and 40 PD by PACT at remote distance, distance, or near (101 in BLR group, 96 in R/R group)

Technical plan

1. Limit the patient-level dataset ROSTER to patients where the STRATUM variable from tblStratum, the variable used to stratify the randomization, = 'Basic IXT with 15-40PD angle'

Dataset used: ROSTER

274
275
276

Objective #2: Determine the cumulative probability of meeting each of the three cause-specific suboptimal surgical outcome criteria by 3 years (post hoc outcome)

277
278
279
280
281
282
283
284
285
286
287
288

1. Define three causes of meeting suboptimal surgical outcome:
 - Exotropia suboptimal outcome criterion
 - Constant esotropia suboptimal outcome criterion
 - Stereoacuity suboptimal outcome criterion
2. Calculate patient-level cause-specific suboptimal surgical outcomes.
3. Get cumulative probability of each cause-specific suboptimal surgical outcome by 3 years for each treatment group from Kaplan-Meier (K-M) survival analysis.
4. Compare cumulative probability of each cause-specific suboptimal surgical outcome by 3 years between treatment groups using a two-sided Z-test.
5. Calculate the treatment group difference (and 95% CI) in the cumulative probability of each cause-specific suboptimal surgical outcome 3 years.

289
290

Technical plan

291
292
293
294
295
296
297
298
299
300
301
302

1. Define three causes of meeting suboptimal outcome criteria:
 - **Exotropia** at distance OR near at any time during the exam (i.e., can be constant or intermittent; determined by a cover/uncover test) with a magnitude of atleast 10 PD by SPCT, confirmed by a retest
 - **Constant esotropia** at distance OR near (determined by at least 3 cover/uncover tests—one must be before any dissociation) with a magnitude of atleast 6 PD by SPCT, confirmed by a retest
 - Decrease in Preschool Randot near **stereoacuity** atleast 2 octaves (atleast 0.6 log arcsec) (*see Table 3*) from the enrollment measurement, or to nil, confirmed by a retest

Table 1: Preschool Randot Stereotest

Baseline stereoacuity at enrollment, in arcsec	Level needed at follow up visit to meet surgical failure criteria, in arcsec
40''	200'' or worse
60''	400'' or worse
100''	400'' or worse
200''	800'' or worse
400''	Nil

303
304
305
306
307
308
309

311
312

level time-to-event outcome for meeting the criterion at any time by 3 years.

Rules for Classification of Each Cause Specific Outcome

- a. Patients who meet the specified criterion at any time without having first undergone reoperation are counted as having met the outcome the first time the specific outcome occurs, regardless of whether any other suboptimal surgical outcome criterion was met at any time.

2. For each of these three causes, create a separate patient -

- 313 b. Patientswhounderogoreoperationwithoutfirstmeetingthespecifiedcriterion will be considered
 314 not to have met the outcome and will be censored at the reoperation date month (i.e. the
 315 end of their ‘uncontaminated’ time).
- 316 c. Patientswhodonotmeetthespecifiedcriterionby3yearsandhavenotundergonereoperation are right-
 317 censored for the specified outcome at the last visit date.
- 318
- 319 d. Patientswhomeetcriteriaotherthanthespecifiedcriterion(e.g.exotropiaorconstant esotropiawhen
 320 consideringthestereoasthespecificoutcome) continue to be ‘at risk’ for the specified criterion
 321 provided they have not been reoperated, and are eventually classified as either a, b, or c
 322 above.
 323

324 Because the primary outcome of suboptimal surgical outcome relates to the first occurrence of
 325 deterioration by any method (exotropia, constant esotropia, or stereoacuity loss), need to create the
 326 following for each patient
 327

- 328 • Whether/when they meet stereo deterioration regardless of whether exotropia and/or
 329 constant esotropia deterioration were met first.
- 330 • Whether/when they meet exotropia deterioration regardless of whether constant esotropia
 331 and/or stereo deterioration were met first.
- 332 • Whether/when they meet constant esotropia deterioration regardless of whether exotropia
 333 and/or stereo deterioration were met first.
- 334 • Use the existing verified MASKEDEXAMS dataset created for the ESA 2017 presentation,
 335 which has one-record per maskedexam and defines whether stereo SSO criteria has been met
 336 at the specified masked exam.

```
337 /* VERIFIED MASKEDEXAMS DATASETS CREATED AT TIME OF ESA 2017 PRESENTATION */
338 libname ixtlprev 'F:\user\PEDIG\Manuscripts-
339 Presentations\Manuscripts\IXT\IXT1\Manuscripts\Primary MS\Datasets\8-23-17
340 (verified)';
341
```

342 **Using STEREO suboptimal surgical outcome as an example:**

- 343 • the verified MASKEDEXAMS dataset (one record per masked exam) contains a flag variable
 344 (STEREODETER) to indicate whether stereo deterioration was met at that visit. If stereo
 345 deterioration is met at the visit, the visit type (6, 12, ...36 months) (STEREODETERVISIT)
 346 and the date of the visit (STEREODETERDT) are also defined.
 - 347 • For each patient, obtain from the MASKEDEXAMS dataset the first record at which stereo
 348 deterioration was met.
 - 349 • Merge stereo deterioration flag, date, and visit from this record into the one record per patient
 350 dataset ROSTER.
- 351
- 352
- 353 3. Run Kaplan-Meier survival analysis on cause-specific outcome
- 354 a. Run Kaplan-Meier survival analysis using proc lifetest, specifying the method as Kaplan-
 355 Meier. Use same K-M macro as was used for primary outcome.
 - 356 b. Output survival probabilities and confidence intervals to a dataset.
 - 357 c. Create failure estimates and confidence intervals.
- 358
- 359
- 360

```

361
362 /*****
363 CREATE MACRO TO GET K-M CUMULATIVE PROBABILITY OF A GIVEN OUTCOME BY 3 YEARS
364 *****/
365
366 %macro kmestimates (outcome, outcometime);
367
368 title1 "K-M Survival Analysis for '&outcome' Outcome";
369
370 proc lifetest data = roster method=km outsurv=failresults stderr plots=none alpha=.05;
371     time &outcometime*&outcome(0);
372     strata trtgroup;
373
374 run;
375
376 data failresultCIs;
377     set failresults;
378     /* create failure estimates (rather than survival)*/
379     failure = round ((1-survival), 0.01);
380     failureLCL = round ((1-SDF_UCL), 0.01);
381     failureUCL = round ((1-SDF_LCL), 0.01);
382     /* limit to records where the survival estimate has changed
383     (i.e. records where the CI is not null) */
384     if SDF_LCL NE . then output;
385     label failure = "Cum. probability of '@outcome' Outcome";
386     label failureLCL = "Lower limit of CI for Cum. probability of '@outcome' Outcome";
387     label failureUCL = "Upper limit of CI for Cum. probability of '@outcome' Outcome";
388
389 run;
390 %sort (failresultCIs, trtgroup);
391 proc print data = failresultCIs;
392     by trtgroup;
393     title2"Review Output Dataset from K-M Survival Analysis for '&outcome' Outcome";
394 run;
395
396 %mend;

```

3. Compare cumulative probability of each cause-specific outcome by 3 years for each treatment group using code to perform a Z-test. Manually input probabilities and standard error for each outcome (get from K-M output).

```

402 /* Calculate Z-Test */
403
404 /* Need to manually input probabilities and standard error for each outcome
405 (get from K-M output) */
406
407 data check;
408     length outcome $20;
409     input outcome probblr seblr probrr serr;
410     datalines;
411     exofail 0.#### 0.#### 0.#### 0.####
412     conesofail 0.#### 0.#### 0.#### 0.####
413     stereofail 0.#### 0.#### 0.#### 0.####
414 ;
415
416 run;
417
418 /* note that 0.#### is a placeholder for use in SAP. Actual values taken from K-M output */
419
420 data check;
421     set check;
422     diff = probblr - probrr;
423     sumofsquaredse = sqrt (seblr**2+serr**2);
424     cilower = diff - (1.96*sumofsquaredse);
425     ciupper = diff + (1.96*sumofsquaredse);

```

```
424         zscore = diff/sumofsquaredse;
425         pvalue = 2*(1 - probnorm(abs(zscore)));
426     run;
427
428     proc print data = check noobs;
429         var outcome probblr seblr probrr serr sumofsquaredse diff cilower ciupper zscore pvalue;
